Effect of Dialysis Membranes on Inflammatory and Immune Processes in Hemodialysis

Document Date: July 27th, 2018

Study Group

A total of 52 patients older than 18 years and under 65 years of age who have been undergoing hemodialysis for more than 3 months will be included in the study. The planned study time is 6 months. Patients will be randomized in two groups by a computer program. 26 patients were dialyzed by high-flux dialyzer and 26 patients by middle cut-off dialyser for 3 months. At the end of the third month, the dialysers will be crossing in the same groups. The study will end in three months after crossover.

Clinical Evaluation

All patients will be dialyzed according general recommendations with Kt/Vurea higher than 1.4. The dialysate flow rate and pump speed will be maintained at the recommended values according to the patient's vascular access pathway. Serum samples will be taken at 0 (beginning), 4th (90th day) and 7th (180th day) months in the beginning and at the end of dialysis. Blood count, electrolytes, serum albumin and total protein levels will be determined at 0, 4th and 7th months. Urea, creatinine, albumin, free light chain kappa and lambda, β 2 microglobulin, myoglobin levels will be examined; Kt/Vurea values will be calculated. Between the two groups, serum light chain kappa, serum light chain lambda and β 2 microglobulin and myoglobin levels will be compared. The decrease in serum albumin values over time will be compared between the two groups.

Anti-human CD4, anti-human CD4, anti-human CD16, anti-human CD19, and anti-human CD14 / CD45 fluorescent-labeled monoclonal antibodies will be used for immunophenotyping with flow-cytometry. Cell Quest (BD) and FlowJo analysis programs will be used for data analysis to determine cell groups.

Peripheral blood mononuclear cells will be isolated to determine IL-17A (Th17), IL-10 (Treg), IFN gamma and TNF alpha (Th1) and IL-4 (Th2) intracellular cytokine contents. Cells from culture will be staining with anti-CD3, anti-CD4, anti-CD8 and anti-CD25 monoclonal antibody to determine cell surface molecule expressions, and then undergo intracellular cytokine staining.

IL-17A, IL-10, IFN-gamma, TNF-alpha, IL-18, MCP-1, NLRP3, RANTES and calcification, which are specific for T cell subtypes by ELISA and luminex (multi-bead) method and evaluated as a marker of inflammation simultaneously in patient sera. The FGF-23 levels will be determined according to the manufacturer's instructions.

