Statistical Analysis

The clinical and demographic characteristics of the patients were determined by the Student t-test if the distribution of the continuous variables was normal, if not with the Mann-Whitney U test; categorical variables will be compared with chi-square test. Kappa and lambda levels, serum albumin levels, Kt / V, FGF-23, intracellular cytokine levels if the distribution is normal with Student's t-test and if not with the Mann-Whitney U test. In cases where more than two groups have flow cytometry, ANOVA and Tukey's post-hoc test will be compared with Student's t-test in two groups.

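### Every patient receives both dialysers, but the marker levels are assigned independent-samples tests that ignore the crossover and leave open how the two periods are combined

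*Combined protocol and SAP*

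**What the plan says.** The Study Group section enrols "A total of 52 patients older than 18 years and under 65 years of age", randomises them 26 and 26 to the two dialysers for three months, and then switches them: "At the end of the third month, the dialysers will be crossing in the same groups". The study ends three months later. The Clinical Evaluation section fixes the sampling: "Serum samples will be taken at 0 (beginning), 4th (90th day) and 7th (180th day) months". Day 90 therefore closes the first period and day 180 the second.

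The Statistical Analysis section assigns tests as follows:

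- **Light chains, albumin, Kt/V, FGF-23 and intracellular cytokines:** "Kappa and lambda levels, serum albumin levels, Kt / V, FGF-23, intracellular cytokine levels if the distribution is normal with Student's t-test". The sentence continues with the fallback: "Student's t-test and if not with the Mann-Whitney U test".
- **Flow cytometry:** ANOVA with Tukey's test for more than two groups, otherwise "Student's t-test in two groups".
- **Baseline characteristics:** the same pair, Student's t or Mann-Whitney U.

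Two statements in Clinical Evaluation also bear on the point. For albumin: "The decrease in serum albumin values over time will be compared between the two groups". For the middle molecules: "microglobulin and myoglobin levels will be compared". The Statistical Analysis section names no test for β2-microglobulin, for myoglobin, or for the serum ELISA/Luminex markers other than FGF-23.

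**The concern.** A crossover lets each patient act as his or her own control, and the planned tests do not use this. Mann-Whitney U is an independent-samples test, so naming it as the fallback, with the same pair used for baseline characteristics, marks the t-test as the two-sample form. A paired plan would normally name a signed-rank test.

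The word group is never tied to dialyser, sequence or visit. The two natural readings are:

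- **(a) One visit, 26 against 26.** The standard error is valid, but the within-patient contrast is discarded.
- **(b) Both periods pooled by dialyser, 52 against 52.** Every patient is in both samples. With positive within-patient correlation the computed standard error is too large.

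Under either, a real dialyser effect on light chains, FGF-23 or cytokines may be reported as no difference when the collected data could have shown it. Because the combination rule is open, the same data can also yield different results in different hands.

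**Working it through.** **Inputs.** From the Study Group section: 52 patients, 26 per sequence, two periods. The sample size comes with no alpha, power, effect size or SD, so there is no planning figure to reproduce.

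**Assumptions.** Two-sided alpha 0.05, SD = 1, complete data, equal correlation ρ between any two visits at 0.3 / 0.5 / 0.7, and no carryover unless stated. Power is from the noncentral t distribution for (a), the crossover analysis and ANCOVA, and from the normal distribution for (b).

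**Variance of the estimated dialyser difference**

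- Reading (a): 2/26, SE 0.277, 50 df.
- Crossover (half the difference between sequences in mean period difference): 2(1−ρ)/52, SE 0.164 / 0.139 / 0.107, 50 df.
- Ratio (a) to crossover: 2/(1−ρ) = 2.9 / 4.0 / 6.7.
- Reading (b): the test assumes SE √(2/52) = 0.196, but the true SE is √(2(1−ρ)/52). The overstatement is 1/√(1−ρ) = 1.20 / 1.41 / 1.83.

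**Detectable difference at 80% power.** Reading (a): 0.79 SD. Crossover: 0.47 / 0.40 / 0.31 SD.

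**Power at ρ = 0.3 / 0.5 / 0.7**

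| True effect | (a) 26 v 26 | (b) 52 v 52 pooled | Crossover analysis |
|---|---|---|---|
| 0.4 SD | 29% | 53 / 53 / 54% | 67 / 81 / 95% |
| 0.5 SD | 42% | 75 / 79 / 85% | 85 / 94 / 99.5% |
| 0.8 SD | 81% | over 99% | over 99% |

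The flat column for (b) at 0.4 SD arises because its rejection threshold is 1.983 × √(2/52) = 0.389 SD, almost the assumed effect.

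**Type I error.** Reading (a) holds 5% (simulated 4.9 to 5.2%). Reading (b) is conservative: 2Φ(−1.983/√(1−ρ)) = 1.8 / 0.5 / 0.03%, and simulation gives 2.1 / 0.6 / 0.04%.

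**Period effect.** With d = 0.5 SD and ρ = 0.5, a period shift of 0.5 SD lowers simulated power for (b) from 79% to 75%. The crossover analysis stays at 94%.

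**Albumin change.** If the decrease runs from day 90 to day 180, comparing it between sequences is already the crossover contrast. If it runs from day 0 to day 90, its variance is 4(1−ρ)/26. That is four times the crossover's (1−ρ)/26 at any ρ, and the detectable difference is 0.94 / 0.79 / 0.61 SD.

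**Carryover.** If a fraction c of the first-period effect persists to day 180, the crossover estimate becomes d(1−c/2). For d = 0.4 SD:

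- c = 0.25: estimate 0.35 SD, power 55 / 70 / 89%.
- c = 0.50: estimate 0.30 SD, power 43 / 56 / 78%.
- Day-90 ANCOVA on day 0, unaffected by carryover: variance 2(1−ρ²)/26, 49 df, power 32 / 37 / 51%.

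**The case against.** The strongest reply is that the sentence on the markers has no main verb and names neither groups nor visits, so the same tests could be meant for within-patient differences. A two-sample t-test or rank-sum test on period differences between sequences would be sound. But the sentence speaks of levels, and only albumin is described as a change, without time points. If differences are intended, the plan has to say so.

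A second reply is that the loss under (b) depends on the effect size. That stands: at 0.8 SD it is negligible. Under (a) it is not, at 81% against over 99%, and the documents give no reason to expect an effect that large. Reading (a) also loses without any correlation: at ρ = 0 its variance is twice the crossover's (power 42% against 71% at 0.5 SD).

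A third is that power is not the only possible cost. This also stands, and it counts against the plan. An analyst who tests the groups at each visit and accepts either result has a false-positive rate of about 8 to 10% in simulation. One who compares the randomised groups on the average of both periods cancels the dialyser effect.

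Finally, with no washout described, a crossover analysis may be biased toward no effect. The carryover figures above show this. Even at 50% persistence, though, its power (43 / 56 / 78%) exceeds the 29% of the unadjusted single-visit test.

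**Conclusion.** The concern holds. The tests named for the marker levels do not fit a two-period crossover, and the contrast they are to test is not defined. If within-patient correlation is positive, neither (a) nor (b) inflates false positives; both lose power. At 0.4 SD the shortfall against a crossover analysis is 38 / 52 / 66 percentage points for (a) (67, 81 and 95 minus 29) and 14 / 28 / 41 for (b) (67, 81 and 95 minus 53, 53 and 54), at correlations of 0.3 / 0.5 / 0.7.

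The mismatch is read directly from the documents. The size of the loss rests on assumed correlation, effect size, complete data and negligible carryover. The plan should be changed before the data are analysed.

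**What to change.** In the Statistical Analysis section:

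1. Make the main analysis a linear mixed model of the day-90 and day-180 values, with dialyser, period and sequence as fixed effects and a random patient effect. Fit it separately to start- and end-of-dialysis samples. With complete data this matches a two-sample t-test on day 180 minus day 90 between sequences. A rank-sum test on those differences can serve as the non-parametric check.
2. Analyse skewed markers on the log scale and report a geometric mean ratio with 95% CI.
3. Apply the same analysis to β2-microglobulin, myoglobin and the serum ELISA/Luminex markers. Define the albumin change on the same basis.
4. State what the groups are in the flow cytometry ANOVA. If they are dialyser-by-visit cells, the repeated measurements on each patient must be modelled there too.
5. Add a day-90 between-group ANCOVA adjusted for day 0 as a carryover-free sensitivity analysis. State in advance that the crossover model is primary and that the two will be compared by estimate and confidence interval. With ANCOVA power of 32 to 51% at 0.4 SD, its non-significance alone says little.

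The cost is SAP wording and a little more analysis. All the samples are already planned, so no new data, visits or patients are needed. The price is reliance on small carryover, which is why item 5 is reported alongside.

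### The trial is a two-period crossover, but the Statistical Analysis section names no within-patient method, and the flow-cytometry ANOVA/Tukey rule refers to more groups than are randomised

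*Combined protocol and SAP*

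**What the plan says.** The Study Group section sets the design. "Patients will be randomized in two groups by a computer program", with 26 patients starting on each dialyser, and "At the end of the third month, the dialysers will be crossing in the same groups". A further three months follow. No washout is described.

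The Clinical Evaluation section gives the measurement times: "Serum samples will be taken at 0 (beginning), 4th (90th day) and 7th (180th day) months", with blood count and chemistry on the same months. The cell-assay paragraphs give methods but no times: "fluorescent-labeled monoclonal antibodies will be used for immunophenotyping with flow-cytometry", and "Cell Quest (BD) and FlowJo analysis programs will be used for data analysis to determine cell groups". The section also promises a longitudinal comparison: "The decrease in serum albumin values over time will be compared between the two groups".

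The Statistical Analysis section then assigns tests. Free light chains, albumin, Kt/V and FGF-23 go to a normality-dependent pair of tests, as do "intracellular cytokine levels if the distribution is normal with Student's t-test and if not with the Mann-Whitney U test". Flow cytometry has its own rule: "In cases where more than two groups have flow cytometry, ANOVA and Tukey's post-hoc test will be compared with Student's t-test in two groups". The section mentions no paired test, mixed or repeated-measures model, or period, sequence or carry-over term.

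**The concern.** The design pays for within-patient information, since every patient is observed on both dialysers, but no named analysis is set up to use it. Mann-Whitney U is an independent-samples test. It uses the pairing only if it is given within-patient differences, which the plan does not say. Student's t-test is not labelled paired or unpaired.

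The cytometry sentence adds a second difficulty. ANOVA with Tukey is reserved for more than two groups, but randomisation creates two. Any larger set has to be built from visits, group-by-visit cells or cell populations, and the same patients then appear in several of the groups. The usual one-way ANOVA treats those values as independent and puts between-patient variation in the error term.

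The likely loss is sensitivity. A moderate dialyser effect on cell subsets, cytokines or solutes could be missed although the design could show it. The choice between a one-visit, a pooled and a within-patient comparison is also left open until the data are in hand.

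**Working it through.** **What can be reproduced.** 26 + 26 = 52 agrees with the stated total. The documents give no alpha, power, effect size, SD or correlation, so the sample size can be neither confirmed nor refuted.

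**Inputs.** From the Study Group section: 26 patients per sequence, two periods. Assumed for illustration: two-sided alpha 0.05, SD 1, normal data, a dialyser effect of 0.4 SD, correlation ρ between a patient's values at different visits, no period effect, no dropout, and no carry-over unless stated.

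**Three ways to test the dialyser effect, at ρ = 0.5**

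1. *Crossover (within-patient).* SE = √(2(1 − ρ)/52) = √(1/52) = 0.139. Effect/SE = 0.4/0.139 = 2.88, against a critical t(50) of 2.009. Power is about 81%.
2. *Unpaired t-test on 52 + 52 values.* The test uses SE = √(2/52) = 0.196, so the estimate must exceed 1.983 × 0.196 = 0.389. The estimate's true SE is 0.139, so power ≈ Φ((0.400 − 0.389)/0.139) = Φ(0.08), about 53%. True type I error ≈ 2(1 − Φ(1.96/√0.5)) = 0.0056; simulation gives about 0.007. Nominal is 0.05, so the test is conservative.
3. *Two randomised groups at day 90 only.* SE = √(2/26) = 0.277. Effect/SE = 0.4/0.277 = 1.44, against 2.009. Power is about 29%.

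**Dependence on the assumptions** (power from 40,000 simulated trials per setting, crossover / unpaired pooled):

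| Effect | ρ = 0 | ρ = 0.3 | ρ = 0.5 | ρ = 0.7 |
|---|---|---|---|---|
| 0.2 SD | 17 / 17% | 22 / 13% | 30 / 9% | 45 / 5% |
| 0.4 SD | 52 / 53% | 67 / 54% | 81 / 53% | 95 / 54% |
| 0.6 SD | 85 / 86% | 95 / 90% | 99 / 93% | 100 / 97% |
| 0.8 SD | 98 / 98% | 100 / 99% | 100 / 100% | 100 / 100% |

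At ρ = 0 the crossover gains nothing, and at 0.8 SD its gain is under one point.

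**ANOVA over three repeated values.** Suppose three values per patient are treated as independent groups. Simulated type I error of the one-way ANOVA is then about 1.4%, 0.4% and 0.02% at ρ = 0.3, 0.5 and 0.7. It is again conservative when repeat values are positively correlated.

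**Carry-over.** If a share c of the first-period dialyser difference persists at day 180, the crossover estimate becomes effect × (1 − c/2). At 0.4 SD and ρ = 0.5:

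- c = 0.25: 0.4 × 0.875 = 0.35 SD, power about 70%.
- c = 0.50: 0.4 × 0.75 = 0.30 SD, power about 57%.
- c = 1.00: 0.4 × 0.50 = 0.20 SD, power about 29%.

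The day-90 test stays at about 29% throughout, because nothing precedes the first period. Adjusting day 90 for day 0 raises its power to about 37% at ρ = 0.5.

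**The case against.** The strongest reply is that the Clinical Evaluation section, apart from its mention of cell populations, uses the word groups for the two randomised groups. The natural reading of the two-group clause is then 26 against 26 at a visit, and that is a valid test. The ANOVA clause is conditional and may never be invoked. The unpaired pooled t-test in the illustration is described nowhere in the plan, and the effect size and correlation are assumed. With no washout described, the crossover's advantage also depends on carry-over being small. All of this stands. It narrows the point to lost efficiency and an unspecified comparison, and it rules out saying that every independent-samples test here has the wrong error term.

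Three stronger readings are tempting, and the documents do not support them.

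- *The plan inflates false positives.* A reader might infer this from negatively correlated cell subsets, or from pooling days 90 and 180 within each randomised group. But a dialyser comparison uses the same subset at two visits, and negative correlation between different subsets in one sample says nothing about that. Nothing in the text suggests pooling both visits within randomised groups.
- *The plan commits to treating repeated values as independent.* It does not say so. It only fails to name any method that would do otherwise.
- *The trial has no sampling schedule.* It has one, at 0, 90 and 180 days for serum and on the matching months for routine bloods. The text also describes serum inflammatory markers as measured simultaneously, directly after the cell assays. That the cell assays share these visits is a reasonable inference, but it is not stated.

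**Conclusion.** The point holds as a mismatch between design and analysis. The design is a two-period crossover, no within-patient or crossover method is named for any outcome, and the cytometry rule provides for more groups than randomisation creates. If it is applied as independent-groups ANOVA/Tukey to visits, group-by-visit cells or cell populations, the error term is wrong. If only one visit is compared, the test is valid but discards the crossover.

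At 0.4 SD and correlation 0.5 without carry-over, the crossover analysis gains 81 − 53 = 28 percentage points of power over the unpaired pooled test and 81 − 29 = 52 over the day-90 test. These figures illustrate the cost under assumed values and do not estimate this trial's power. The undefined cytometry groups and times are, by themselves, matters for clarification. Overall this is a cheap improvement, held with medium confidence.

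**What to change.** - For each repeated outcome, including each cell subset, pre-specify one within-patient dialyser contrast adjusted for period. A mixed model with dialyser, period and sequence terms and a random patient effect would serve, as would the equivalent two-period crossover t-test.
- Keep a route for non-normal data, as the plan does now: a rank-based crossover test or a transformation.
- Take any comparison across visits, with its Tukey adjustment, from a repeated-measures model.
- State the no-carry-over assumption, since no washout is described. Report the day-90 first-period comparison, adjusted for day 0 where sampled, as a sensitivity analysis that carry-over cannot affect.
- As clarification, state the cytometry sampling times and what the groups are when there are more than two.

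The cost is revised SAP wording, slightly more analysis work and reliance on the no-carry-over assumption for the main contrast. No extra patients are needed, and no extra samples if cytometry is already planned at days 90 and 180.
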